4.3.5 Investigational Medicinal Product Accountability

All IMPs required for completion of this study (MSTT1041A and placebo) will be provided by the Sponsor where required by local health authority regulations. The study site will acknowledge receipt of IMPs supplied by the Sponsor using the IxRS to confirm the shipment condition and content. Any damaged shipments will be replaced.

IMPs will either be disposed of at the study site according to the study site's institutional standard operating procedure or be returned to the Sponsor (if supplied by the Sponsor) with the appropriate documentation. The site's method of destroying Sponsor-supplied IMPs must be agreed to by the Sponsor. The site must obtain written authorization from the Sponsor before any Sponsor-supplied IMP is destroyed, and IMP destruction must be documented on the appropriate form.

Accurate records of all IMPs received at, dispensed from, returned to, and disposed of by the study site should be recorded on the Drug Inventory Log.

4.3.6 Continued Access to MSTT1041A

Currently, the Sponsor (Genentech, a member of the Roche Group) does not have any plans to provide Genentech IMP MSTT1041A or any other study treatments or interventions to patients who have completed the study. The Sponsor may evaluate whether to continue providing MSTT1041A in accordance with the Roche Global Policy on Continued Access to Investigational Medicinal Product, available at the following website:

http://www.roche.com/policy_continued_access_to_investigational_medicines.pdf

4.4 CONCOMITANT THERAPY, PROHIBITED THERAPY, AND ADDITIONAL RESTRICTIONS

Concomitant therapy consists of any medication (e.g., prescription drugs, over-the-counter drugs, vaccines, herbal or homeopathic remedies, nutritional supplements, emollients) used by a patient in addition to protocol-mandated treatment from 6 months before screening. All such medications should be reported to the investigator and recorded on the Concomitant Medications eCRF.

4.4.1 Cautionary Therapy

4.4.1.1 Herbal Therapies

Concomitant use of herbal therapies is not recommended because their pharmacokinetics, safety profiles, and potential drug–drug interactions are generally unknown. However, herbal therapies may be used during the study at the discretion of the investigator.

4.4.2 Prohibited Therapy

Use of the following concomitant therapies is prohibited at any time after enrollment in the double-blind treatment period, unless otherwise indicated as described below (see Sections [4.1.1](#) and [4.1.2](#) for inclusion and exclusion criteria):

- Investigational therapy (other than protocol-mandated study treatment)
- Treatment with TCS or TCIs
- Treatment with a licensed biologic agent
- Treatment with immunomodulatory/immunosuppressive (e.g., systemic corticosteroids, methotrexate, mycophenolate-mofetil, IFN- γ , Janus kinase inhibitors, cyclosporine, azathioprine)
- Treatment with immunoglobulin or blood products
- Treatment with any live attenuated vaccines
- Initiation of or change in allergen immunotherapy
- Initiation of or change in treatment of AD with prescription moisturizers or moisturizers containing additives such as ceramide, hyaluronic acid, urea, or filaggrin degradation products

Note: Patients should continue using stable doses of such moisturizers if initiated at least 1 week before the randomization visit

- Initiation of therapy with bleach baths
- Regular use (more than 2 visits per week) of a tanning booth/parlor
- Phototherapy

4.4.3 Additional Restrictions

Patients will have to fast for at least 8 hours prior to collection of blood samples for fasted glucose and lipids for select visits (see [Appendix 1](#) for timepoints). If patient has not fasted for 8 hours, the patient must return to the site for fasting blood draw.

4.5 STUDY ASSESSMENTS

The schedule of activities to be performed during the study is provided in [Appendix 1](#). All activities should be performed and documented for each patient.

Patients will be closely monitored for safety and tolerability throughout the study. Patients should be assessed for toxicity prior to each dose; dosing will occur only if the clinical assessment and available laboratory test values are acceptable.

All assessments must be performed on the day of the specified visit unless otherwise specified in the schedule of activities (see [Appendix 1](#)). As much as feasible, the disease severity assessments (EASI, IGA, and SCORAD) for each patient should be administered by the same assessor throughout the study. The assessments should

be performed by the investigator but may be administered by other site staff who are qualified and trained to perform the assessment, if approved by the Sponsor.

4.5.1 Informed Consent Forms and Screening Log

Written informed consent for participation in the study must be obtained before performing any study-related procedures (including screening evaluations). Informed Consent Forms for enrolled patients and for patients who are not subsequently enrolled will be maintained at the study site.

All screening evaluations must be completed and reviewed to confirm that patients meet all eligibility criteria before enrollment. The investigator will maintain a screening log to record details of all patients screened and to confirm eligibility or record reasons for screening failure, as applicable.

4.5.2 Medical History, Concomitant Medication, and Demographic Data

Medical history, including clinically significant diseases, surgeries, cancer history, reproductive status, smoking history, and use of alcohol and drugs of abuse, will be recorded at baseline. In addition, all medications (e.g., prescription drugs, over-the-counter drugs, vaccines, herbal or homeopathic remedies, nutritional supplements, emollients) used by the patient within 6 months before screening will be recorded. At the time of each follow-up physical examination, an interval medical history should be obtained and any changes in medications and allergies should be recorded.

Demographic data will include age, sex, and self-reported race/ethnicity.

4.5.3 Atopy Status

The patient's atopy status (atopic or non-atopic) will be assessed during screening on the basis of historical documentation (e.g., patient's medical records). A patient is considered atopic if he or she has a positive result to any allergen demonstrated via historical allergy test (e.g., skin prick [wheal diameter ≥ 3 mm and documented negative control]), ImmunoCAP®, or other specific IgE test. Regardless of atopy status, total and specific IgE testing will be performed as specified in [Appendix 1](#).

4.5.4 Physical Examinations

A complete physical examination, performed at screening and other specified visits, should include an evaluation of the head, eyes, ears, nose, and throat, and the cardiovascular, dermatologic, musculoskeletal, respiratory, gastrointestinal, and neurologic systems. Any abnormality identified at baseline should be recorded on the General Medical History and Baseline Conditions eCRF.

Limited, symptom-directed physical examinations should be performed at specified postbaseline visits and as clinically indicated. Changes from baseline abnormalities

should be recorded in patient notes. New or worsened clinically significant abnormalities should be recorded as adverse events on the Adverse Event eCRF.

4.5.5 Vital Signs

Vital signs will include measurements of respiratory rate, pulse rate, and systolic and diastolic blood pressure, ideally while the patient is in a seated position, and temperature.

4.5.6 Laboratory, Biomarker, and Other Biological Samples

Samples for the following laboratory tests will be sent to the study site's local laboratory for analysis or analyzed at point of care:

- Urine pregnancy test for all women of childbearing potential

Urine pregnancy tests will be performed at the site prior to each administration of study drug and at other specified visits after treatment discontinuation. If a local urine pregnancy test result is positive, it must be reported immediately, and study drug will not be administered that day. The positive urine pregnancy result must be confirmed by a serum pregnancy test (conducted by the central laboratory). Refer to Section 5.4.3.1 for management of a patient with a positive pregnancy test.
- TB tests: PPD or QFT (QFT may be conducted by the central laboratory, per Sponsor agreement with site)

Samples for the following laboratory tests will be sent to one or several central laboratories for analysis:

- Hematology: WBC count, RBC count, hemoglobin, hematocrit, platelet count, and differential count (neutrophils, eosinophils, basophils, monocytes, lymphocytes, other cells)
- Chemistry panel (serum or plasma): bicarbonate or total carbon dioxide (if considered standard of care for the region), sodium, potassium, chloride, glucose, BUN or urea, creatinine, total protein, albumin, phosphorus, calcium, total and direct bilirubin, ALP, ALT, AST
- Fasting lipids: total cholesterol, LDL cholesterol, HDL cholesterol, triglycerides
- Fasting glucose
- HbA_{1c}
- N-terminal pro B-type natriuretic peptide
- Serum pregnancy test
- Urinalysis, including dipstick (pH, specific gravity, glucose, protein, ketones, blood) and microscopic examination (sediment, RBCs, WBCs, casts, crystals, epithelial cells, bacteria)

- Viral serology: HBsAb, HBsAg, HBCAb, HCV antibody
 - If HBsAb testing is positive and HBCAb is positive, patient must undergo further testing for HBV DNA.

Blood samples will be collected to evaluate the pharmacokinetics of MSTT1041A in serum as noted in the schedule of activities (see [Appendix 1](#)). Serum concentrations of MSTT1041A will be determined using validated analytical procedures.

The following samples will be sent to the Sponsor or a designee for analysis:

- Serum samples for MSTT1041A PK analysis
- Serum samples for immunogenicity analysis
- Serum samples for specific IgE, and total IgE, and other biomarkers; mandatory blood

For sampling procedures, storage conditions, and shipment instructions, see the laboratory manual.

Unless the patient gives specific consent for his or her leftover samples to be stored for [REDACTED] biological samples will be destroyed when the final Clinical Study Report has been completed, with the following exceptions:

- Serum samples collected for PK or immunogenicity analysis may be needed for PK or immunogenicity assay development and validation; therefore, these samples will be destroyed no later than 5 years after the final Clinical Study Report has been completed.
- Blood [REDACTED] research will be destroyed no later than 10 years after the final Clinical Study Report has been completed.

When a patient withdraws from the study, samples collected prior to the date of withdrawal may still be analyzed, unless the patient specifically requests that the samples be destroyed or local laws require destruction of the samples. However, if samples have been tested prior to withdrawal, results from those tests will remain as part of the overall research data.

Data arising from sample analysis, including data on germline mutations, will be subject to the confidentiality standards described in Section 8.4.

Given the complexity and exploratory nature of exploratory biomarker analyses, data derived from these analyses will generally not be provided to study investigators or patients unless required by law. The aggregate results of any conducted research will be available in accordance with the effective Sponsor policy on study data publication.

4.5.7 Electrocardiograms

Single ECG recordings will be obtained at specified timepoints, as outlined in the schedule of activities (see [Appendix 1](#)), and may be obtained at unscheduled timepoints as indicated.

All ECG recordings must be performed using a standard high-quality, high-fidelity digital electrocardiograph machine equipped with computer-based interval measurements. Lead placement should be as consistent as possible. ECG recordings must be performed after the patient has been resting in a supine position for at least 10 minutes. All ECGs are to be obtained prior to other procedures scheduled at that same time (e.g., blood draws). Circumstances that may induce changes in heart rate, including environmental distractions (e.g., television, radio, conversation) should be avoided during the pre-ECG resting period and during ECG recording.

For safety monitoring purposes, the investigator must review, sign, and date all ECG tracings. Paper copies of ECG tracings will be kept as part of the patient's permanent study file at the site. Digital recordings will be stored at central ECG laboratory, and the data will be sent to the Sponsor, using the Sponsor's standard procedures to handle and process the electronic transfer of these data. Any clinically significant morphologic waveform changes or other ECG abnormalities must be documented on the appropriate eCRF. If considered appropriate by the Sponsor, ECGs may be analyzed retrospectively at a central laboratory.

If at a particular postdose timepoint the mean QTcF is > 500 ms and/or > 60 ms longer than the baseline value, another ECG must be recorded, ideally within the next 5 minutes, and ECG monitoring should continue until QTcF has stabilized on two successive ECGs. The same procedure should be repeated approximately 30 minutes after QTcF has stabilized on two successive ECGs of the first measurement. The Medical Monitor should be notified. Standard-of-care treatment may be instituted per the discretion of the investigator. If a PK sample is not scheduled for that timepoint, an unscheduled PK sample should be obtained. A decision on study drug discontinuation should be made, as described in Section [5.1.2.3](#). The investigator should also evaluate the patient for potential concurrent risk factors (e.g., electrolyte abnormalities, co-medications known to prolong the QT interval, severe bradycardia).

4.5.8 Chest X-Rays

Patients with a positive PPD (without a history of Bacillus Calmette-Guérin vaccination) or a positive or indeterminate QFT will require a chest X-ray to review for evidence of active TB, including posteroanterior and lateral views, unless a chest X-ray has been

performed within 3 months before screening and the report is available for review. A chest computed tomography scan may substitute for a chest X-ray. Chest X-rays should only be performed if patients first meet all other study eligibility criteria. All imaging should be read by a radiologist or per local requirements.

4.5.9 Clinician-Reported and Patient-Reported Outcomes

Clinician-reported outcome (ClinRO) and patient-reported outcome (PRO) data will be collected via questionnaires to document the treatment benefit of MSTT1041A. The questionnaires, translated into the local language as appropriate, will be completed in their entirety at specified timepoints during the study. To ensure instrument validity and that data standards meet health authority requirements, questionnaires will be self- or interviewer-administered before the patient receives any information on disease status, prior to the performance of non-PRO assessments, and prior to the administration of study treatment, unless otherwise specified. Adverse event reports will not be derived from PRO or ClinRO data by the Sponsor, and safety analyses will not be performed using PRO or ClinRO data. All adverse events should be recorded as described in Section 5.

Patients and clinicians will use an electronic device to capture PRO and ClinRO data. The electronic device and/or instructions for completing the questionnaires electronically will be provided by site staff. The data will be transmitted to a centralized database maintained by the electronic device vendor. The data will be available for access by appropriate study personnel.

4.5.9.1 Eczema Area and Severity Index

EASI is a clinician-reported comprehensive measure of disease that is composed of individual components (i.e., body region involvement, severity) that can be separated and evaluated independently or in combination to provide a more complete assessment of the patient (see [Appendix 4](#)). EASI evaluates four anatomical regions (head/neck, upper limbs, trunk, lower limbs) for both the affected BSA and severity of key disease signs (erythema, induration, excoriation, lichenification).

4.5.9.2 SCORing Atopic Dermatitis, Clinician Reported

The SCORAD has clinician-reported and patient-reported assessments. The clinician-reported assessments require physician-assessed intensity ratings for six signs/symptoms of AD (erythema, edema/papulation, oozing/crust, excoriation, lichenification, and dryness), which are each weighted by the percentage of the BSA affected. This clinician-rated score is augmented with patient-reported assessments ranging from 0–10 of both pruritus and sleep loss.

The patient-reported symptom components of SCORAD are single-item assessments of itch and sleep that use a 3-day recall period. They can be found in [Appendix 5](#).

4.5.9.3 Investigator Global Assessment

The IGA is a clinician-reported assessment using a 0–4 point scale to capture the IGA of AD (see [Appendix 6](#)). The IGA severity scale will be dichotomized to success or failure, with success defined as a score of clear (0) or almost clear (1) with at least two grades reduction from baseline score.

MSTT1041A—Genentech, Inc.
44/Protocol GS40965, Version 1

MSTT1041A—Genentech, Inc.
45/Protocol GS40965, Version 1

4.6 TREATMENT, PATIENT, STUDY, AND SITE DISCONTINUATION

4.6.1 Study Treatment Discontinuation

Patients must permanently discontinue study treatment if they experience any of the following:

- Any medical condition that the investigator or Sponsor determines may jeopardize the patient's safety if he or she continues to receive study treatment
- Investigator or Sponsor determination that treatment discontinuation is in the best interest of the patient
- Pregnancy
- Cases of potential drug-induced liver injury that include an elevated ALT or AST in combination with either an elevated bilirubin or clinical jaundice, as defined by Hy's Law (see Section 5.3.5.8)

The primary reason for study treatment discontinuation should be documented on the appropriate eCRF. Every effort should be made to retain patients in the study. All patients will be asked to complete all study visits and assessments regardless of discontinuation of study treatment. Patients who discontinue study treatment prematurely will not be replaced.

4.6.2 Patient Discontinuation from Study

Patients have the right to voluntarily withdraw from the study at any time for any reason. In addition, the investigator has the right to withdraw a patient from the study at any time. Reasons for withdrawal from the study may include, but are not limited to, the following:

- Patient withdrawal of consent
- Study termination or site closure
- Any patient that the investigator or Sponsor considers lost to follow up

Every effort should be made to obtain information on patients who withdraw from the study but have not withdrawn consent. The primary reason for withdrawal from the study should be documented on the appropriate eCRF. If a patient requests to be withdrawn from the study, this request must be documented in the source documents and signed by the investigator. Patients who withdraw from the study will not be replaced.

If a patient is unable to complete all study visits and assessments (see Section [4.6.1](#)), the patient should be asked to return to the clinic for an early termination visit. This visit should occur approximately 4 weeks after the final dose of study drug (see [Appendix 1](#), for study assessment details).

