5.3.1 Adverse Event Reporting Period

Investigators will seek information on adverse events at each patient contact. All adverse events, whether reported by the patient or noted by study personnel, will be recorded in the patient's medical record and on the Adverse Event eCRF.

After informed consent has been obtained but prior to initiation of study drug, only serious adverse events caused by a protocol-mandated intervention (e.g., invasive procedures such as biopsies, discontinuation of medications) should be reported (see Section [5.4.2](#) for instructions for reporting serious adverse events).

After initiation of study drug, all adverse events will be reported until 12 weeks after the final dose of study drug.

Instructions for reporting adverse events that occur after the adverse event reporting period are provided in Section [5.6](#).

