5.4.2.2 Events That Occur after Study Drug Initiation

After initiation of study drug, serious adverse events and adverse events of special interest will be reported until 12 weeks after the final dose of study drug. Investigators should record all case details that can be gathered immediately (i.e., within 24 hours after learning of the event) on the Adverse Event eCRF and submit the report via the electronic data capture (EDC) system. A report will be generated and sent to Safety Risk Management by the EDC system.

In the event that the EDC system is unavailable, the paper Clinical Trial Serious Adverse Event/Adverse Event of Special Interest Reporting Form provided to investigators should be completed and submitted to the Sponsor or its designee immediately (i.e., no more than 24 hours after learning of the event), either by faxing or by scanning and emailing the form using the fax number or email address provided to investigators. Once the EDC system is available, all information will need to be entered and submitted via the EDC system.

Instructions for reporting serious adverse events that occur > 12 weeks after the final dose of study treatment are provided in Section 5.6.

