5.4.3 Reporting Requirements for Pregnancies

5.4.3.1 Pregnancies in Female Patients

Female patients of childbearing potential will be instructed to immediately inform the investigator if they become pregnant during the study or within 12 weeks after the final dose of study drug. A paper Clinical Trial Pregnancy Reporting Form should be completed and submitted to the Sponsor or its designee immediately (i.e., no more than 24 hours after learning of the pregnancy), either by faxing or by scanning and emailing the form using the fax number or email address provided to investigators. Pregnancy

should not be recorded on the Adverse Event eCRF. The investigator should discontinue study drug and counsel the patient, discussing the risks of the pregnancy and the possible effects on the fetus. Monitoring of the patient should continue until conclusion of the pregnancy. Any serious adverse events associated with the pregnancy (e.g., an event in the fetus, an event in the mother during or after the pregnancy, or a congenital anomaly/birth defect in the child) should be reported on the Adverse Event eCRF. In addition, the investigator will submit a Clinical Trial Pregnancy Reporting Form when updated information on the course and outcome of the pregnancy becomes available.

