6.1 DETERMINATION OF SAMPLE SIZE

Approximately 90 patients in total will be randomized in a 1:1 ratio to 490 mg SC MSTT1041A or placebo Q4W. The sample size provides at least 80% power to detect a difference of 34% in the percent change from baseline in EASI score at Week 16 between MSTT1041A- and placebo-treated patients, assuming a standard deviation of 40.6 for placebo-treated patients. The same number of patients can also provide at least 80% power to detect 1) a difference of 27% between MSTT1041A- and

placebo-treated patients in the proportion of patients achieving IGA scores of 0 or 1 at Week 16, assuming the percentage is 2% in placebo-treated patients, respectively, 2) a difference of 32% between MSTT1041A- and placebo-treated patients in the proportion of patients achieving EASI-75 at Week 16, assuming the percentage is 13% in placebo-treated patients, and 3) a difference of 30% between MSTT1041A- and placebo-treated patients in percent change from baseline to Week 16 in pruritus NRS, assuming a standard deviation of 37.3 for placebo-treated patients. The sample size is calculated at a two-sided significance level of 0.05 and assumes 25% dropout.

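### Patients who leave the study have no scheduled contact after the early-termination visit at about 4 weeks, although adverse events are to be reported to 12 weeks after the last dose

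*Combined protocol and SAP*

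**What the plan says.** Four parts of the protocol bear on this point.

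- **Exit visit.** Under Section 4.6.2, when someone cannot complete all visits, "the patient should be asked to return to the clinic for an early termination visit". On timing: "This visit should occur approximately 4 weeks after the final dose of study drug". Appendix 1, footnote a, repeats this.
- **Reporting window.** Section 5.3.1: "After initiation of study drug, all adverse events will be reported until 12 weeks after the final dose of study drug". Section 5.4.2.2: "serious adverse events and adverse events of special interest will be reported until 12 weeks after the final dose of study drug". The Appendix 1 footnotes on concomitant medications and adverse events use the same 12-week limit.
- **How events are found.** Section 5.3.1: "Investigators will seek information on adverse events at each patient contact".
- **Pregnancy.** Under Section 5.4.3.1, women of childbearing potential are "instructed to immediately inform the investigator if they become pregnant during the study or within 12 weeks after the final dose of study drug". Section 5.4.3.2 gives male patients the same instruction about their partners.

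Sections 4.3.2.1, 4.3.4 and 4.6.1 separately ask patients who stop study drug or receive rescue treatment to continue with study visits and assessments. Section 4.6.2 also asks sites to pursue information on withdrawn patients whose consent still stands.

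**The concern.** Active enquiry depends on contacts, and the contacts run out at different times for different patients. A completer is asked about adverse events until the 12-week window closes. A patient who leaves the study is last asked at about 4 weeks, and Appendix 1 shows nothing afterwards except an optional unscheduled visit.

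Section 6.5 summarises adverse-event incidence by treatment arm. Section 6.2 summarises number of doses and duration of treatment, but not the time over which events were sought. If study withdrawal differs between arms, the two incidences rest on different amounts of active follow-up, and no planned table would show it. With about 45 patients per arm, a few unrecorded events, including the events of special interest named in Section 5.2.3, could change how the safety comparison reads.

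**Working it through.** **Inputs**

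- Doses on Day 1 and at Weeks 1, 4, 8 and 12, that is Days 1, 8, 29, 57 and 85 (Appendix 1).
- End-of-study visit at Week 24, Day 169 (Appendix 1).
- Visit windows of ±4 days at Week 12 and ±5 days at Week 24 (Appendix 1).
- Early-termination visit about 4 weeks (28 days) after the final dose (Section 4.6.2).
- Reporting window of 12 weeks (84 days) after the final dose (Section 5.3.1).
- About 90 patients; the sample-size calculation "assumes 25% dropout" (Section 6.1).

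**Step 1: does the schedule deliver the 12-week window for a completer?**

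(169 − 85) / 7 = 84 / 7 = 12.0 weeks. It does. At the extremes of the visit windows:

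- shortest: (164 − 89) / 7 = 75 / 7 = 10.7 weeks
- longest: (174 − 81) / 7 = 93 / 7 = 13.3 weeks

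So the schedule and the window agree for completers, apart from normal visit tolerance.

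**Step 2: what does a leaver get?**

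12 − 4 = 8 weeks after the early-termination visit, or 8 / 12 = 67% of the window, with no scheduled contact.

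| Final dose | Early-termination visit (+28 days) | Window closes (+84 days) | Contacts in between if the patient had stayed |
|---|---|---|---|
| Day 1 | Day 29 | Day 85 | Days 43, 57, 71, 85 |
| Week 1 (Day 8) | Day 36 | Day 92 | Days 43, 57, 71, 85 |
| Week 4 (Day 29) | Day 57 | Day 113 | Days 71, 85, 99, 113 |
| Week 8 (Day 57) | Day 85 | Day 141 | Days 99, 113, 141 |
| Week 12 (Day 85) | Day 113 | Day 169 | Days 141, 169 |

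Whatever the final dose, a patient who stays has two to four scheduled contacts in the interval, and a patient who leaves has none.

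**Step 3: when is the gap smaller?**

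- Last dose at Week 12, last contact at Week 20: (169 − 141) / 7 = 4 weeks uncovered.
- Last dose at Week 4, still attending until Week 20: (141 − 29) / 7 = 16 weeks of follow-up after the dose, so nothing is uncovered.

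Eight weeks is therefore the gap for a patient whose last contact is the early-termination visit at its stated time.

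**Step 4: how many patients?**

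0.25 × 90 = 22.5, so about 22. If all of them left at the early-termination visit, the time without scheduled enquiry would be 22.5 × 8 = 180 patient-weeks, out of 90 × 12 = 1,080 patient-weeks after the final dose, or 17%. Both figures are ceilings. The 25% is a sample-size allowance that says nothing about when patients leave or whether they take the exit visit.

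**The case against.** The strongest reply is that nothing here is contradictory. One rule sets how long events must be reported and the other sets when an exit examination takes place, and a site can follow both. The duty in Section 5.3.1 covers events reported by patients as well as those noted by staff, and it does not end at the exit visit. Section 4.6.2 tells sites to pursue information after withdrawal. Events already recorded are followed to resolution or stability (Section 5.5.1), and the sponsor may telephone about serious events, events of special interest and pregnancies (Section 5.5.2).

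Much of this stands, and it rules out several stronger readings that a reader might infer:

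- **That events in leavers cannot be collected after 4 weeks.** They can. What is missing is a scheduled enquiry.
- **That patients who stop for intolerance fall into the gap.** Section 4.3.2.1 asks them to continue assessments, and Section 4.6.1 asks all who stop treatment to complete all visits. Only leaving the study opens the gap.
- **That pregnancies go uncaptured.** Patients are instructed to report them to 12 weeks. The difference is that a completer also has a urine test at Week 24, while a leaver's last scheduled test is at the exit visit.
- **That late hypersensitivity is the main loss.** Section 5.1.1.2 says such effects typically occur within hours of dosing, although they may be delayed.

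What the reply does not answer is the difference in method. Follow-up of recorded events does not find new ones. An instruction with no date, method or content will be carried out differently from site to site, and it is not equivalent to the direct questioning that completers receive.

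**Conclusion.** The point holds in this form: for patients who leave the study, the protocol sets a 12-week reporting window and schedules contact for only about the first 4 weeks of it. Up to 8 weeks (67%) then rest on spontaneous report and an unspecified effort.

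This assumes that the early-termination visit takes place at its stated time and is the last contact. Later leavers have a shorter gap or none. The number affected is at most about 22 of 90. It should not be read as a forecast, and fewer could be reached in practice, because withdrawal of consent and loss to follow-up are among the reasons for leaving listed in Section 4.6.2.

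A reader might also infer that the safety comparison is biased in favour of one arm. The documents do not support that: they give no withdrawal rates by arm, so neither the direction nor the size of any bias can be stated. The primary efficacy analysis is not involved. This is an inexpensive improvement to safety ascertainment, not a defect that undermines the trial.

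**What to change.** Reconcile Section 4.6.2 and Appendix 1, footnote a, with Sections 5.3.1, 5.4.2.2 and 5.4.3.

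1. For patients who leave the study without withdrawing consent to contact, add one telephone contact at 12 weeks after the final dose, covering adverse events, pregnancy and concomitant medications. Section 3.1 already provides telephone visits on health status and medications, so the format exists.
2. In Section 6.5, report adverse-event follow-up time by arm beside incidence, measured from first dose to the last adverse-event enquiry, so that unequal ascertainment can be seen.

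The cost is one schedule footnote, one summary table and at most about 22 calls, some of which will be declined or unanswered. The study need not be longer: for the latest scheduled dose the window closes on Day 169, which is already the nominal day of a completer's final visit. A call prompts a pregnancy report but does not replace the Week 24 urine test, so that difference from completers would remain.
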